3.7.2 Pulmonary Function Tests (PFTs)

PFTs include the following parameters: forced expiratory volume in one second (FEV₁), forced vital capacity (FVC), FEV₁/FVC, and diffusing capacity of the lungs for carbon monoxide (DLCO).

Values, absolute changes from baseline, and percent change from baseline will be presented at each scheduled visit by treatment and overall. Any value of FEV₁/FVC larger than 1 will be excluded from the summary table but included in the listing.

The DLCO (mL.min⁻¹.mmHg⁻¹) will be evaluated as below:

$$DLCO_{Male} = \exp(-7.664278 + 2.151173 \ln(\text{height}) - 0.027927 \ln(\text{age}) + Mspline)$$

$$DLCO_{Female} = \exp(-7.914474 + 2.171106 \ln(\text{height}) - 0.025634 \ln(\text{age}) + Mspline)$$

The height and age are expressed as centimeters and years, respectively. The Mspline values are collected from the supplementary documents of article Stanojevic S, Graham BL, Cooper BG, et al. Official ERS technical standards: Global Lung Function Initiative reference values for the carbon monoxide transfer factor for Caucasians.

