- b Participants who terminate the stu y prematurely early termination "ET" will un ergo all activities as escribe un er D673 with the exception of dosing.
- c Day 30 will always be the day after Day 29, regardless of when Day 29 occurs within the  $\pm$  2-day visit window

- d Any visit marke with a "P" in the "Visit" row can be complete as a phone visit. The Investigator can choose to have site visits on these days if deemed necessary.
- e The first dose of study intervention must be administered at the clinical site.
- f Post-bronchodilator values for DLCO and spirometry (FEV1 and FVC) will be recorded. The order of testing for recorded values should be 1) administer bronchodilator, 2) immediately perform DLCO, and 3) perform spirometry. On dosing days, DLCO and spirometry will be performed predose.
- g Collect and record the number and severity of pulmonary exacerbations since the last PFT assessment, resting peripheral oxygen saturation, smoking status including number of cigarettes per day, and use of AAT replacement therapy since the last visit. Assess and record the Modified Medical Research Council dyspnea scale.
- h For Dose 1 only, blood samples for hematology, clinical chemistry, and coagulation studies will be collected predose and at 6 hours (± 30 minutes) postdose. At other dosing visits, these samples will only be collected predose. See Section 10.2 for a detailed list of clinical laboratory parameters.
- i A urine pregnancy test will be performed prior to dosing. If the result is positive, a confirmatory serum pregnancy test will be performed. Dosing should not occur unless a negative result is obtained with the confirmatory serum pregnancy test in consultation with the Sponsor.
- j Samples for complement analysis will be collected surrounding Dose 1 only. For Dose 1, samples will be collected predose, at 2 and 6 hours (±30 minutes), and 24 hours (±1 hour) postdose. At EOT, samples will be collected at the same time as all other sample collections.
- k The AFP sample should be collected predose.
- 1 Urine sample will be collected predose.
- m The serum AAT and CRP samples should be collected predose. Blood samples for determination of CRP will be collected at the same time as those for determination of serum AAT.
- n At all visits, the blood sample for antidrug antibodies will be collected predose.
- o Blood samples for biomarkers of fibrosis will be collected predose on dosing days.

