### 2.3.1.2. Risks Related to AAT Knockdown

There is currently little experience with AAT knockdown in patients with PiZZ AATLD. However, the knockdown of AAT could potentially worsen the related loss-of-function effects in the lungs, since it has been shown that subjects with Null mutations of the *SERPINA1* gene and thereby no Z-AAT production, are at a particularly high risk of emphysema. It is however important to note that the pulmonary manifestations in the Null mutation population usually develop after decades of total absence of the AAT protein (Fregonese et al, 2008).

In the DCR-A1AT-101 study, a mean knockdown of 78% was achieved and no clinically significant changes in lung function were noted on spirometry or DLCO, no dose-dependent changes were noted in repeat measurements of any spirometry parameter, and all Percent Predicted DLCO measurements remained within normal limits across all cohorts.

In addition, others have reported that no clinically meaningful changes in spirometry were observed after 40 weeks (N=16) or 72 weeks (N=4) of Z-AAT knockdown in patients with AATLD (Strnad et al., 2021).

To mitigate this risk, serial measurements of PFTs will be conducted throughout the study, and whenever applicable augmentation therapy will be able to restore absent serum AAT protein concentrations and anti-neutrophil elastase capacity to levels at the lower limit of normal (Wewers, 1987; Sandhaus et al., 2016; Chapman et al., 2015; Sorrells et al., 2015).

In study participants already on augmentation therapy at the initiation of the study, the risk of worsening the loss-of-function disease mechanism in the lungs is reduced because these study participants have non-mutated M-AAT levels restored to the lower limit of normal and this would not be affected by the Z-AAT knockdown (Chapman KR, Chorostowska-Wynimko J, Koczulla AR, Ferrarotti I, McElvany NG. Alpha 1 antitrypsin to treat lung disease in alpha 1 antitrypsin deficiency recent developments and clinical implications. Int J Chron Obstruct Pulmon Dis. 2018;13:419-432.

).

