### 8.2.2. Physical Examinations

A complete physical examination will be required at visits as indicated in the SoA (Section 1.3) and will include, at a minimum, assessments of the eyes, ears, nose, throat, thyroid/neck, lymph nodes, as well as cardiovascular, respiratory, gastrointestinal, musculoskeletal, dermatological, and neurological systems. Height (in cm, only at Screening), weight (in kg), and body mass index will also be measured and recorded. Height and weight should be measured without shoes.

In lieu of a complete physical examination, a focused physical examination will be performed at other visits indicated in the SoA (Section 1.3). It will include, at a minimum, assessments of the skin, lungs, cardiovascular system, and abdomen (liver and spleen).

Investigators should note any pre-existing clinical signs related to previous illnesses.

For at-home visits (whenever applicable), the home-health nurse will provide in-person support to the Investigator in assessing the participant.

Study intervention injection sites should be inspected at each visit.

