### 8.2.5.2. Diffusion Capacity of the Lungs for Carbon Monoxide

Definition:

 DLCO is a measure of the quantity of CO transferred per minute from alveolar gas to red blood cells (specifically hemoglobin) in pulmonary capillaries. DLCO is expressed as mL/min/mmHg, that is, the milliliters of CO transferred per minute for each millimeter of mercury in pressure difference across the total available functioning lung gas exchange surface.

Procedure:

- DLCO will be performed per the ATS/ERS standards (Graham et al., 2017). The same calibrated equipment must be utilized throughout the study.
- DLCO will be performed prior to spirometry testing.
- Participants should be seated throughout the procedure and should be allowed several minutes of quiet breathing prior to testing to become accustomed to the mouthpiece and nose clip. A minimum of 2 acceptable maneuvers should be completed, with values within 2.00 mL/min/mmHg (0.67 mmol/min/kPa) of each other. Participants should be given a 4-minute window between maneuvers to allow for adequate

elimination of the test gas from the lungs. Not more than 5 maneuvers should be attempted.

Full details regarding the conduct of and the criteria for acceptability of DLCO will be provided in a separate manual.

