# 9.3. Statistical Analyses

#### 9.3.1. Analyses of Primary Endpoints

#### 9.3.1.1. Safety Analysis

All safety analyses will be performed on the Safety Population. Adverse events will be defined as TEAEs if they have a start date on or after the administration of study drug during the treatment period, or if they occur prior to the administration of study drug and worsen in severity/grade or relationship to the study intervention after the administration of study intervention during the treatment period. Frequency and percentages will be used to summarize TEAEs, SAEs, and AEs of special interest by relationship. Laboratory values will be reported by grade and summarized, if applicable.

Change from baseline and observed values will be summarized where applicable. Laboratory analytes will be presented by a shift from baseline and graphically represented in mean values over time where applicable. Vital signs, ECG, and PFTs (i.e., FEV1, FVC, FEV1/FVC, and DLCO) will be summarized as continuous parameters.

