The study will include 3 cohorts. In Cohorts 1 and 2 there will be up to 8 participants in each cohort (randomization scheme ratio of 3:1 active: placebo). The sample size for Cohort 1 and Cohort 2 is based on clinical consideration rather than statistical power calculation.

The primary endpoint for Cohort 3 of this study is the percentage change from baseline in serum and liver Z-AAT protein concentration at week 24. Assuming the percentage change from baseline is 80%, 60% and 10% in the active high dose group, active low dose group and placebo group respectively, and the standard deviation is 0.5 for all three groups, a sample size of 10 participants per treatment group will provide at least 80% power to detect a statistically significant difference between active high dose group and placebo, and between active low dose group and placebo, at an overall 1-sided significance level of 0.05.

The F1/F2, F3, and F4 fibrosis types will be used as randomization stratification factors for all 3 cohorts.

2.3 **Study Endpoints**

2.3.1 *Primary Endpoints*

The primary endpoints for Cohorts 1 and 2 are:

- The incidence and nature of treatment emergent adverse events (TEAEs), and the change from Baseline in pulmonary function tests (PFTs), 12-lead electrocardiograms (ECGs), physical examination (PE) findings, vital signs, and clinical laboratory tests
- Changes from baseline to weeks 24 (Cohort 1)/ 48 (Cohort 2) in serum AAT protein concentrations

The primary endpoints for Cohort 3 are:

- Change from baseline to week 24 in serum AAT protein levels
- Change from baseline to week 24 in liver AAT protein levels

2.3.2 *Secondary Endpoints*

The secondary endpoints are:

- PK profile of belcesiran
- Change from baseline up until week 96 in liver fibrosis
- Change from Baseline up until week 96 in diastase-resistant PAS-positive AAT globules

2.3.3 *Exploratory Efficacy Endpoints*

The exploratory endpoints are:

- Change from Baseline up until week 96 in FibroScan® score
- Change from Baseline up until week 96 in enhanced liver fibrosis (ELF) score
- Change from Baseline up until week 96 in cytokeratin 18 (CK-18)

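### As written, SAP 3.7.2 obtains DLCO from a reference equation in sex, height and age, and never says that the measured DLCO is what is summarised

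*SAP*

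**What the plan says.** **SAP.** Section 3.7.2 names four parameters: FEV1, FVC, FEV1/FVC and DLCO. For all of them it promises values, absolute changes and percent changes from baseline at each scheduled visit. For DLCO it adds "The DLCO (mL.min⁻¹.mmHg⁻¹) will be evaluated as below" and gives one equation for men and one for women. The inputs are height in cm, age in years and an Mspline term taken from the supplement of an outside article, whose title describes "Global Lung Function Initiative reference values for the carbon monoxide transfer factor for Caucasians". Section 2.3.1 makes "the change from Baseline in pulmonary function tests (PFTs), 12-lead electrocardiograms (ECGs" and other safety measures part of the primary endpoint for Cohorts 1 and 2.

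**Protocol.** Section 8.2.5.2 treats DLCO as a test result: "DLCO is a measure of the quantity of CO transferred per minute from alveolar gas to red blood cells". The schedules in section 1.3 state that "Post-bronchodilator values for DLCO and spirometry" are recorded. Section 9.3.1.1 calls for observed values and changes from baseline, and lists the PFTs "and DLCO) will be summarized as continuous parameters". Height is recorded once, according to section 8.2.2: "Height (in cm, only at Screening".

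**The concern.** The left-hand side of each SAP equation is DLCO itself, in the unit of the measured test. The right-hand side contains no measurement of gas transfer. Two participants of the same sex, height and age would be given the same value whatever their tests showed, and within a participant almost nothing can change between visits.

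Protocol 2.3.4 names decline in lung function as a key potential risk. The SAP performs no hypothesis tests, so the descriptive tables carry the safety reporting. A DLCO table built from this rule would be nearly flat, or would follow a lookup table, and could reassure wrongly.

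**Working it through.** The documents state no DLCO figure to reproduce. The check evaluates the printed equations and asks what can move the result between visits.

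**Inputs from the documents**
- Men: DLCO = exp(-7.664278 + 2.151173 ln(height) - 0.027927 ln(age) + Mspline)
- Women: DLCO = exp(-7.914474 + 2.171106 ln(height) - 0.025634 ln(age) + Mspline)
- Eligible age 18 to 75 years (protocol 5.1); height fixed at its Screening value (protocol 8.2.2); treatment to week 96.

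**Assumptions, not in the documents**
- Height 175 cm (men) and 163 cm (women).
- Mspline 0 at baseline, varied below. The SAP gives neither its values nor what it depends on.
- Age advances with the visit: 96 / 52.18 = 1.84 years. The SAP does not say whether age is taken at baseline or at the visit.

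**Step 1: level at age 50, Mspline 0.**
- Man: exp(-7.664278 + 2.151173 × ln 175 - 0.027927 × ln 50) = 28.13 mL/min/mmHg.
- Woman: the second equation at 163 cm gives 21.00.
- With Mspline from -0.2 to +0.2, the levels run from 23.0 to 34.4 (man) and 17.2 to 25.6 (woman).

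**Step 2: change from baseline with Mspline constant.** Height and Mspline cancel, leaving

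percent change = 100 × [((age + t) / age)^(-b) - 1], with b = 0.027927 (men) or 0.025634 (women).

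For a man aged 50 at week 96: 100 × [(51.84 / 50)^(-0.027927) - 1] = -0.101%.

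| Baseline age | Men, week 96 | Women, week 96 |
|---|---|---|
| 18 | -0.271% | -0.249% |
| 30 | -0.166% | -0.152% |
| 40 | -0.126% | -0.115% |
| 50 | -0.101% | -0.093% |
| 61 | -0.083% | -0.076% |
| 75 | -0.068% | -0.062% |

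Across both sexes the range is -0.139% to -0.031% at week 48 and -0.070% to -0.016% at week 24. If age and Mspline are both fixed at baseline, the change is exactly 0.

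**Step 3: scale.** For the 50-year-old man the 96-week change is -0.03 mL/min/mmHg. A true 15% fall from the same level would be 0.15 × 28.13 = 4.2.

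**Step 4: if Mspline changes between visits by δ.** The percent change becomes 100 × [exp(δ) × ((age + t) / age)^(-b) - 1]. For the 50-year-old man at week 96, assumed shifts of -0.10, -0.05 and +0.05 give -9.6%, -5.0% and +5.0%. To print a 15% fall, δ would have to be about ln 0.85 = -0.16. Any such movement would come from the lookup table and not from the participant's test.

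**The case against.** The strongest reply is that no sensible programmer would follow the literal text. For a test done at each visit, values naturally means results. FEV1 and FVC are not called measured in 3.7.2 either, and nobody doubts what is meant there. The cited source is a set of reference values, which points to a predicted quantity, and the protocol reports for the earlier study that "all Percent Predicted DLCO measurements remained within normal limits across all cohorts". Protocol 9.3.1.1 asks for observed values. SAP section 6 claims no deviation from the protocol analysis, although it cites v3.0 and the protocol supplied is Version 4.0. SAP section 7 puts all available data in listings. The trial was also stopped early, with at most 16 participants and descriptive analysis only.

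Much of this stands. The equations were probably meant as predicted values, and the text does not prove that measured DLCO will be missing from the outputs. The Mspline shifts in step 4 are illustrative. The 4.2 mL/min/mmHg is a scale and not an event under protocol 7.1.1.1, which also requires an absolute fall above 6.5.

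It does not remove the defect. DLCO, unlike FEV1 and FVC, has its own instruction, and that instruction gives the reference equation under the name and unit of the test. The SAP sections on laboratory tests, vital signs and ECGs do say actual or observed values. On the charitable reading the rule is still unusable: the output is not labelled as predicted, no percent predicted is defined, and the age to use is not stated.

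**Conclusion.** The concern holds as a statement about the written rule. SAP 3.7.2 defines DLCO by an equation that contains no measurement, which conflicts with protocol 8.2.5.2 and 9.3.1.1. If it is followed, the DLCO change-from-baseline table shows between 0 and -0.27% over 96 weeks with Mspline constant, or otherwise tracks the lookup table, whatever happens to gas transfer. The sizes rest on the printed coefficients and, for absolute levels, on assumed height and Mspline. That no measurement enters needs no assumption.

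This should be fixed because it affects a component of the primary safety endpoint. Its reach is limited: FEV1, FVC, FEV1/FVC, data collection, participant listings and the individual rule in protocol 7.1.1.1 are untouched, and no hypothesis test depends on the table.

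**What to change.** Replace the DLCO text in SAP 3.7.2 with wording to this effect: *Measured post-bronchodilator DLCO is the variable summarised (values, absolute change and percent change from baseline, by visit and treatment). The equations below give predicted DLCO and are used only for percent predicted = 100 × measured / predicted, with age taken at [baseline or visit, to be stated].*

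Optionally, also summarise Hb-corrected DLCO, the measure used in protocol 7.1.1.1. The SAP would then have to say how the correction is obtained and which version is the numerator of percent predicted. If percent predicted is not wanted, the equations can be dropped.

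The cost is SAP wording and one derived variable, or a second if an Hb-corrected value has to be derived. Measured DLCO and hemoglobin are already collected, so no new data are needed. If the database is already locked, the clarification belongs in the CSR, as SAP section 1 provides.

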3.7.3 Clinical Laboratory Tests

Results of clinical laboratory tests will be descriptively summarized as follows: For continuous laboratory parameters, actual values at each scheduled visit (including follow-up visits) and absolute changes from baseline will be summarized. For categorical laboratory parameters, numbers and percentages of participants in each test result category will be presented by visit.

By-participant listings will be presented by clinical laboratory test parameters, values outside the reference ranges will be flagged.

3.7.4 Vital Signs

Vital sign parameters include height, weight, oral temperature, heart rate, respiratory rate, and blood pressure (systolic and diastolic). The observed values at each visit, baseline and absolute change from baseline to post-baseline visits values will be summarized using descriptive statistics. By-participant listing of vital sign parameters will be provided.

3.7.5 Electrocardiograms

Standard 12-lead ECGs will be performed in the supine position after the participant has rested comfortably for 10 minutes. 12-Lead ECGs will be obtained using a machine that automatically calculates the heart rate and ventricular rate and measures RR, PR, QRS, QT, and corrected QT intervals (QTcF, Fridericia correction). For each 12-lead ECG parameter, observed values at each visit, baseline and absolute change from baseline to post-baseline visit values will be summarized using descriptive statistics.

A summary of QTc and QTcF measurements will be performed, within treatment group and time point, using counts and percentages of the number of participants with assessments that meet the following criteria: absolute QTc or QTcF > 500 msec, QTc or QTcF with a change from baseline >60 msec.

For the overall interpretation of the ECG profile, the number and percentage of participants in each category (Normal, Abnormal Not Clinically Significant, or Abnormal Clinically Significant) recorded on the CRF will be presented by visit and by treatment and overall. 12-Lead ECG data will be listed by participants.

3.7.6 *Physical Examinations (PE)*

For the overall interpretation of the PE, the number and percentage of participants in each category (Normal, Abnormal Not Clinically Significant, or Abnormal Clinically Significant) recorded on the CRF will be presented by visit and by treatment and overall. Physical examination data will be listed by participant.

3.7.7 *Other Safety Assessments*

Total complement hemolytic activity (CH50, including C3a, C5a, and Bb), serum alpha fetoprotein (AFP), coagulation parameters (aPTT, PT, and INR), antidrug antibodies, and C-reactive protein will be summarized using descriptive statistics for each visit by treatment and overall. Listings will also be provided.

4 DATA SAFETY MONITORING COMMITTEE

A Data Safety Monitoring Committee (DSMC) will monitor the safety of participants over the course of the study. Table 7 of the protocol shows the minimal required timing of reviews by the DSMC. Ongoing risk-benefit assessments will be conducted throughout the trial by the independent DSMC. In addition, DSMC will provide a comprehensive review of study safety, tolerability, and PK/PD data, along with a summary of cohort reviews across all cohorts and provide decisions. Further operational details will be pre-specified in the DSMC charter.

5 ANALYSIS TIMING

5.1 Interim Analysis

There are no interim analyses planned due to the early termination of the study.

5.2 Final Analysis

The study was terminated prior to enrolling the participants into Cohort 3. The database will be locked after completion of the follow-up for Cohort 1 and Cohort 2 participants. The study will be unblinded at the participant level and the final analysis will be generated. The final analysis will be performed on all available data as described in the above sections of SAP. The corresponding tables, figures, and listings (TFL) will be provided after the database lock.

In addition to TFLs, Study Data Tabulation Model (SDTM) data and ADaM data along with associated files will be provided. Associated files may include the following: annotated CRFs, SDTM specifications, SDTM programs, ADaM specifications, ADaM programs, and TFL programs.

6 CHANGES FROM PROTOCOL-SPECIFIED STATISTICAL ANALYSES

This SAP does not deviate from the statistical analysis described in v3.0 of the protocol. Any deviations from the protocol or SAP will be described in the CSR.

7 PROGRAMMING SPECIFICATIONS

Analyses will be performed using SAS[®] version 9.4 or higher. All available data will be presented in participant data listings which will be sorted by participant and visit date as applicable. Detailed Programming Specifications will be provided in a separate document.
